6.7.5 Adverse Events

Adverse events will be followed as outlined in Section [9.0](#).

6.7.6 Safety Laboratory Tests

The Central Laboratory will be responsible for chemistry, hematology, coagulation, and serum pregnancy testing (per [Table 14](#)), as well as processing and/or storage of other study samples, including the archival tumor samples. Specific instructions for processing, labeling, and shipping

samples will be provided in a Central Laboratory Manual. The date and time of sample collection will be reported to the Central Laboratory.

Local laboratories will be used for dosing decisions. Local laboratory assessments resulting in a dose change or as part of an AE assessment, which is not supported by Central Laboratory results, will be reported on the electronic case report form (eCRF).

Urine pregnancy test will be performed at the site.

Table 14: Blood, Hematology, and Chemistry Evaluations

| Chemistry | Hematology | Other |
|-------------------------|---------------------|---|
| Albumin | WBC | Serum β -hCG or urine pregnancy test ^b |
| Alkaline phosphatase | Hemoglobin | |
| ALT | Hematocrit | |
| AST | Platelet | |
| Bicarbonate | ANC | |
| BUN | | |
| Calcium | Differential | |
| Chloride | Eosinophils | |
| Creatinine ^a | Lymphocytes | |
| Glucose | Monocytes | |
| Lipase | Neutrophils | |
| Magnesium | Coagulation | |
| Phosphorus | PT/INR | |
| Potassium | aPTT | |
| Sodium | | |
| Total bilirubin | | |
| Direct bilirubin | | |
| Total protein | | |
| CA 19-9 | | |

Abbreviations: ALT = alanine aminotransferase; ANC = absolute neutrophil count; aPTT = activated partial thromboplastin time; AST = aspartate aminotransferase; β -hCG = beta-human chorionic gonadotropin; BUN = blood urea nitrogen; INR = international normalized ratio; PT = prothrombin time; WBC = white blood cells.

^aEstimated creatinine clearance (CL_{cr})/glomerular filtration rate will be calculated based on the MDRD formula.

^bFemales of child-bearing potential only. Serum pregnancy will be conducted at Screening. Urine pregnancy will be conducted pre-dose on Day 1 of every odd-numbered cycle.

Blood samples will be obtained at the time points indicated in the SOE ([Appendix A](#)).

At any time during the study, abnormal laboratory parameters that are clinically relevant (eg, lead to clinical symptoms or signs or require therapeutic intervention) and constitute an AE must be recorded in the eCRF.

If a study patient experiences elevated $ALT \geq 5 \times ULN$ and elevated total bilirubin $\geq 2 \times ULN$, or $ALT \geq 8 \times ULN$, liver tests ([Appendix I](#)), including ALT, AST, total bilirubin, direct bilirubin, gamma-glutamyl transferase (GGT), and creatine phosphokinase (CPK), should be repeated within 3 to 5 days to confirm the abnormality and to determine if it is increasing or decreasing. If the abnormality persists or worsens, clinical and laboratory monitoring should be initiated by the investigator, based on the hepatic monitoring tests ([Appendix I](#)) and in consultation with the Lilly Clinical Research Physician (CRP). Monitoring of ALT, AST, and total bilirubin should continue until levels normalize or return to approximate baseline levels.

Lilly will periodically review evolving aggregate safety data within the study by appropriate methods.

6.7.6.1 Pregnancy Test

All females of childbearing potential will have a serum pregnancy test at Screening. Urine pregnancy tests will be performed on Day 1 of each odd-numbered cycle, every 28 days in patients who continue AM0010 monotherapy after FOLFOX discontinuation, at EOT, and 30 days after EOT. The results must be confirmed as negative prior to administration of investigational product.

6.7.6.2 Health Outcomes

The assessment of patient-reported outcomes (PROs), including symptoms, functioning, and health status, will be assessed using the EORTC QLQ-C30 questionnaire (Version 3) and EQ-5D-5L. Both instruments should be administered together at the beginning of the study visit prior to any extensive contact or consultation with study site personnel, which may bias patient responses. The EORTC QLQ-C30 will be presented first, followed by EQ-5D-5L. Patients will only complete either instrument if a validated translation is made available in a language in which the patient is fluent.

The EORTC QLQ-C30 is a self-administered questionnaire that assesses multiple dimensions of HRQoL of cancer patients participating in international clinical trials. The EORTC QLQ-C30 includes 5 functional domains (physical, role, emotional, cognitive, and social), 9 symptom scales (fatigue, nausea and vomiting, pain, dyspnea, insomnia, appetite loss, constipation, diarrhea, and financial difficulties), and global health status/QoL.

The EQ-5D-5L (Rabin et al., 2011) is a PRO measure designed to assess current health status for clinical and economic appraisal. Patients are asked to rate 5 dimensions of HRQoL - Mobility, Self-care, Usual activities, Pain/discomfort, and Anxiety/depression - using 5 ordered response categories:

no problems (1), slight problems (2), moderate problems (3), severe problems (4), and extreme problems (5).

The questionnaires will be completed by all patients as detailed in the SOE ([Appendix A](#)).

6.8 Sample Collection

6.8.1 Collection of Archival Tumor Tissue

Collection of archival tumor material is neither mandatory nor required for eligibility. However, attempts should be to acquire these archival tissue samples, if available, starting after the patient is enrolled. Patients will be asked to consent to the access of pre-existing samples (slides or blocks) (frozen and/or paraffin-embedded tumor samples) for biomarker development. Pathology reports should be obtained if available. Immunohistochemical staining of these tumor samples may be conducted to assess the degree of immune cell infiltration and expression of immune cell surface molecules and cytokines within the tumor. Refer to the Laboratory Manual for additional information. These materials will not be used for any other purpose at the end of the study. Fresh tumor biopsies are not required, but should replace archival tissue if it is not available.

No fresh tumor biopsies are required for participation in the study.

6.8.2 Pharmacokinetic Sample Collection

Lilly will attempt to collect PK samples in patients randomized to ARM 1 and ADA samples from ARM 1 and 2 patients at clinical sites. Patients must give their permission to obtain the additional blood samples as outlined in the ICF. Within each 14-day cycle (with the first day of dosing designated as Day 1).

Blood samples will be obtained as shown in [Table 15](#):

- Cycles 1 and 2, Days 1 and 13
- Cycle 3 Day 1 Only
- Cycle 4 Day 13 Only
- Cycle 5 Day 1 Only
- EOT and follow-up visit 30 days after EOT (ADA only).

In the event of clinical site business hours, weekends, or holiday schedule leading to missed PK/ADA time points, these time points will not need to be made up on a different day. Patients will be instructed to administer AM0010 in the usual manner at home on days of PK sampling. The time at

which AM0010 is administered on that day will be queried by site personnel and entered in the CRF. Dose times for other days will be obtained from the Dosing Diary.

Bioanalytical samples collected to measure investigational product concentration will be retained for a maximum of 1 year following last participant visit for the study.

Table 15: Pharmacokinetic Sparse Sampling Regimens

| Cycle | Day |
|--------------|------------------------|
| 1 and 2 | 1 and 13 of each cycle |
| 3 | 1 Only |
| 4 | 13 Only |
| 5 | 1 Only |

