2.2.1 Treatment Duration

Each cycle is 14 days, with Days 6, 7, 13, and 14 being rest days for AM0010. FOLFOX will be administered on Day 1 of each cycle. Patients randomized to the investigational combination treatment (AM0010 plus FOLFOX) ARM 1, after completion of up to 12 cycles of combination chemotherapy or if experiencing chemotherapy intolerance (as defined as Grade 3 or 4 non-hematologic toxicity that has not resolved to baseline in 28 days or Grade 4 hematologic toxicity that has not resolved to baseline in 28 days) may continue to receive maintenance AM0010 if the patient continues to receive clinical benefit (CR, PR, or SD). Patients may receive FOLFOX on both study arms for up to 12 cycles or 24 weeks. Patients will be treated until tumor progression by RECIST v.1.1.

Patients may continue on treatment until they experience progressive disease, unacceptable toxicity, require palliative radiotherapy, withdraw consent, or their physician feels it is no longer in their best interest to continue on study treatments.

To mitigate the chance of detecting false-progression (ie, pseudoprogression) early in the course of treatment on ARM 1 with AM0010 in combination with FOLFOX, patients whose scans show radiographic progression in the absence of clinical deterioration including worsening ECOG PS as assessed by the Investigator may remain on study treatments and should have an additional scan 4

weeks (± 3 days) later as outlined in Section 8.1.1. If this subsequent scan shows disease progression, the patient will be discontinued from study treatments.

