5.1.3 Dosing Schedule

Patients will be treated on an outpatient basis with AM0010 plus FOLFOX or FOLFOX alone. Each cycle is 14 days.

ARM 1: AM0010 plus FOLFOX

[figure not shown]
AM0010 dose should be administered on Days 1–5 and Days 8–12 in the morning, ideally with 24 hours (± 2 hours) between doses. Days 6, 7, 13, and 14 will be rest days. FOLFOX dosing should be initiated on Day 1 of each cycle, after AM0010 administration on investigational ARM 1 (Figure 7). ARM 2 consists of FOLFOX administration alone as shown below, initiated on Day 1 of a 14-day cycle (Figure 8).

For patients in the combination therapy (AM0010 + FOLFOX) arm, after the last scheduled chemotherapy cycle in the absence of tumor progression, up to 12 cycles, or chemotherapy intolerance, maintenance dosing of AM0010 may continue 5 days on and 2 days off at 10 $\mu\text{g}/\text{kg}$ SQ qd (see Section 5.1.1).

Crossover of patients from the FOLFOX-only treatment arm into the FOLFOX plus AM0010 treatment arm is not permitted. Supportive care per the institution's normal standard of care, including concomitant medications, can be provided at the Investigator's discretion.

[figure not shown]
The documentation of the investigational product administration will be noted on the CRF page and in the source documentation. The date, dose volume, and time of administration for each dose will be recorded in the patient diary and on the respective CRF page. Details of preparing and administering AM0010 will be provided to the patient and are included in the Pharmacy Manual.

Figure 7: ARM 1: AM0010 + FOLFOX

ARM 1 in the absence of tumor progression may continue maintenance with AM0010 alone at either 0.4 mg for patients weighing ≤ 80 kg or 0.8 mg for patients weighing > 80 kg after completion of FOLFOX or FOLFOX intolerance

Figure 8: ARM 2: FOLFOX Alone

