5.2 Dose Interruption, Reduction, and Dose Schedule Modifications

If a non-hematologic AE is attributed to only 1 drug (ie, AM0010, oxaliplatin, or 5-FU), the Investigator should determine if the drug will be continued based on the Investigator's assessment of risk-benefit per the guidelines outlined below. For example, neuropathy, is clearly related to oxaliplatin; therefore, 5-FU/LV as well as AM0010 would not be responsible for this AE.

Hematologic Toxicity Dose Schedule Adjustment Requirements (graded according to the National Cancer Institute Common Terminology Criteria for Adverse Events (NCI CTCAE) v4.03, Appendix G; see also Table 10):

- Thrombocytopenia Grades 3-4 with platelet count $<50,000/\text{mm}^3$: delay treatment with AM0010 and FOLFOX until platelet count returns to $\geq 100,000/\text{mm}^3$. Re-introduction of AM0010 should be administered at 80% and FOLFOX at dose level -1. If on a subsequent cycle these toxicities recur, AM0010 is reintroduced at 60% (-2 dose level) and FOLFOX at dose level -2 after the first recurrence. This will be accomplished by altering the dose schedule from 5 days on and 2 days off to 4 days on and 3 days off (80%), and 3 days on 4 days off (60%), respectively.
- Anemia Grades 3-4 with Hgb <8 g/dL: delay treatment with AM0010 and FOLFOX until Hgb returns to ≥ 10 g/dL. Re-introduction of AM0010 should occur at 80% and FOLFOX at dose level -1. If on a subsequent cycle these toxicities recur, AM0010 is reintroduced at 60% and FOLFOX at dose level -2 after the first recurrence.

Table 10: Hematologic Toxicity Dose Schedule Adjustment (Thrombocytopenia and Anemia Only)

| Occurrence of Hematologic TrAE* | FOLFOX Reintroduction | AM0010 Re-Introduction Dosing | Day 1 (FOLFOX Start) | Day 2 (FOLFOX End) | Day 3 | Day 4 | Day 5 | Day 6 | Day 7 |
|---------------------------------|-----------------------|-------------------------------|----------------------|--------------------|-------|-------|-------|-------|-------|
| – | Full dose | 100% | X | X | X | X | X | Rest | Rest |
| 1 st | –1 | 80% | X | X | X | X | Rest | Rest | Rest |
| 2 nd | –2 | 60% | X | X | X | Rest | Rest | Rest | Rest |

TrAE = Treatment-related Adverse Event; X = dosing

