6.2.1 ARM 1: AM0010 plus FOLFOX

6.2.1.1 AM0010 plus FOLFOX: Cycles 1–12, Day 1

Patients are assigned to ARM 1 dose 5 µg/kg AM0010 SQ on Days 1–5 followed by 2 days off treatment (Day 6 and 7) and 5 µg/kg AM0010 on Day 8–12, followed by 2 days off treatment (Day 13 and 14).

The following procedures and assessments will be performed:

6.2.1.1.1 AM0010 plus FOLFOX: Cycles 1–12, Day 1 (or up to 3 Days Prior) – Pre-Dose

- Clinical evaluations:
 - Physical exam (modified physical examination at odd-numbered cycles capturing changes from prior examinations)
 - ECOG status
 - Weight
 - BSA calculation
- Vital signs (pulse, blood pressure, respiratory rate, and temperature)
- 12-lead ECG (Cycles 1, 2, 3, and 5) pre-dose
- Concomitant medications
- Adverse events
- PK/ADA
 - Cycles 1 and 2, Day 1
 - Cycle 3 Day 1 Only
 - Cycle 5 Day 1 Only
- Patient-reported questionnaires (EORTC QLQ-C30 and EQ-5D-5L) :–data to be collected on Day 1 of every treatment cycle regardless of dosing (including patients receiving AM0010 maintenance therapy) until 30 days after end of treatment (EOT)
- Exploratory Biomarker Cycle 1 Day 1
- Safety laboratory assessments (up to 3 days prior; if screening labs are done within 3 days prior, then screening labs can be used as Day 1 labs):
 - Hematology
 - Serum chemistry
 - Urine pregnancy test (all females of childbearing potential – only on odd-numbered cycles)
- CA 19-9 on Day 1 of every odd-numbered cycle.

Note: In the event the clinical site business hours, weekends, or holiday schedule lead to missed PK/ADA time points, these time points will not need to be made up on a different day.

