6.2.1.1.2 AM0010 plus FOLFOX: Cycles 1–12, Day 1 – Dosing

- Self-administer SQ Injection of AM0010; Dispense AM0010, and AM0010 Dosing Diary
- Administer FOLFOX every 14 days \pm 3 days (Section 5.1.2) for up to 12 cycles.
 - Patients will be treated with AM0010 administered SQ at the research clinic by a qualified staff member in the morning on Study Day 1. The Investigator or a qualified designee must be present during administration. Patients will be trained to self-administer AM0010 and will self-administer the dose daily throughout the study, starting with the first dose on Cycle 1, Day 1.

Note that if the patient is unable or unwilling to self-administer SQ injection of AM0010, the dose may be given by a caregiver.

6.2.1.1.3 AM0010 plus FOLFOX: Cycles 1, 2, and 4, Day 13

The following procedures and assessments will be conducted on Day 13 (\pm 3 days):

- Laboratory assessments (Day 13): CBC and differential with platelet count
- PK/ADA
 - Cycles 1 and 2, Day 13
 - Cycle 4 Day 13 Only
- Exploratory Biomarker Sample Cycle 1 Day 13, Cycle 2 Day 13, and Cycle 4 Day 13
- 12-lead ECG (Cycles 1, 2, and 4)

Note: In the event the clinical site business hours, weekends, or holiday schedule lead to missed PK/ADA time points, these time points will not need to be made up on a different day.

6.2.2 ARM 2: FOLFOX**6.2.2.1 FOLFOX Cycles 1–12: Day 1 (or up to 3 Days Prior) – Pre-Dose**

- Clinical evaluations:
 - Physical examination (modified physical examination at odd-numbered cycles capturing changes from prior examinations)
 - ECOG status
 - Weight
 - BSA calculation

- Vital signs (pulse, blood pressure, respiratory rate, and temperature)
- Concomitant medications
- Adverse events
- Patient-reported questionnaire (EORTC QLQ-C30 and EQ-5D-5L) – data to be collected on Day 1 of every treatment cycle regardless of dosing until 30 days after EOT
- ADA
 - Cycles 1 and 2, Day 1
 - Cycle 3 Day 1 Only
 - Cycle 5 Day 1 Only
- Exploratory Biomarker Cycle 1 Day 1
- Safety laboratory assessments (up to 3 days prior; if screening labs are done within 3 days prior then screening labs can be used as Day 1 labs):
 - Hematology
 - Serum chemistry
 - Urine pregnancy test (all females of childbearing potential – only on odd-numbered cycles)
- CA 19-9 on Day 1 of every odd cycle

Note: In the event the clinical site business hours, weekends, or holiday schedule lead to missed ADA time points, these time points will not need to be made up on a different day.

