- ^c Patients will complete 2 instruments, the EORTC QLQ-C30 and EQ-5D-5L. Both instruments will be administered at baseline (Screening), Day 1 of every treatment cycle regardless of dosing (both during the FOLFOX regimen and during the maintenance cycles), at EOT, and at the follow-up visit 30 days after EOT. Both instruments should be administered together at the beginning of the study visit prior to any extensive contact or consultation with study site personnel, which may bias patient responses. The EORTC QLQ-C30 will be presented first, followed by the EQ-5D-5L.
- ^d Vital signs (pulse, blood pressure, respiratory rate, and temperature) will be collected after being seated or in a semi-recumbent position. Day 1 Treatment vital signs may be performed 1 day prior.

- ^c ECG will be performed in patients seated, semi-recumbent, or supine for at least 5 minutes. A 12-lead ECG should be performed at Screening and EOT (ARM 1 and 2), ARM 1 only at pre-dose Cycles 1, 2, 3, and 5; and on Day 13 on Cycles 1,2, and 4. Day 1 Treatment ECG may be performed 3 days prior.
- ^f Survival Status, every 8 weeks for the first 12 months then every 12 weeks thereafter.
- ^g In patients assigned to AM0010 and FOLFOX (ARM 1), 1 dose of 5 µg/kg AM0010 will be administered daily by SQ injection on Days 1–5 and Days 8–12 of each 2-week cycle. Rest days when AM0010 will not be administered are Days 6–7 and Days 13–14.
- ^h AM0010 study drug and Dosing Diary will be dispensed to patients for self/caregiver administration. The diary will be a part of source documentation and should be reviewed with the patient at every visit. See Pharmacy Manual.
- ⁱ FOLFOX; Day 1 of each 14-day cycle for 12 cycles: *dl*-LV 400 mg/m² and oxaliplatin 85 mg/m² followed by bolus 5-FU 400 mg/m² and a 46- to 48-hour infusion of 5-FU 2400 mg/m².
- ^j PK samples obtained in patients on ARM 1 and ADA samples obtained in patients on ARMs 1 and 2. Samples will be collected during Cycles 1 and 2, Days 1 and 13, Cycle 3 Day 1 only, Cycle 4 Day 13 only, Cycle 5 Day 1 only. ADA will also be collected at EOT and at follow-up visit 30 days after EOT. Blood samples for biomarkers (PD samples) are collected pre-dose on C1D1, C1D13, C2D13, C4D13, and EOT for patients on both arms. See Lab Manual for further details.

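### Protocol 6.8.2 has patients take AM0010 at home on PK sampling days, but nominal Day 13 is a rest day and the Day 1 samples are listed as pre-dose

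*Protocol*

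**What the plan says.** Protocol 6.8.2 sets seven nominal PK time points in ARM 1: Day 1 of Cycles 1, 2, 3 and 5, and Day 13 of Cycles 1, 2 and 4. It then states: "Patients will be instructed to administer AM0010 in the usual manner at home on days of PK sampling". The following sentence concerns the time at "which AM0010 is administered on that day will be queried by site personnel and entered in the CRF". Dose times for all other days come from the Dosing Diary.

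The dosing calendar is fixed elsewhere:

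- Protocol 2.2.1: "Each cycle is 14 days, with Days 6, 7, 13, and 14 being rest days for AM0010".
- Protocol 5.1.3: "Days 6, 7, 13, and 14 will be rest days".
- Appendix A note g: "Rest days when AM0010 will not be administered are Days 6–7 and Days 13–14".
- Protocol 6.2.1.1 gives the same pattern for ARM 1, with dosing on Days 1–5 and 8–12.

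The Day 1 PK samples appear in 6.2.1.1.1 under the heading "AM0010 plus FOLFOX: Cycles 1–12, Day 1 (or up to 3 Days Prior) – Pre-Dose". The next subsection, 6.2.1.1.2, covers Day 1 dosing for Cycles 1–12 and describes AM0010 being given by staff at the research clinic on the morning of Study Day 1. It adds that patients "will self-administer the dose daily throughout the study, starting with the first dose on Cycle 1, Day 1".

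**The concern.** A patient or site coordinator who reads 6.8.2 alone is told to dose on every PK day, and three of those days are rest days. The phrase about the usual manner does not settle the matter. The dose-time sentence asks when the drug was taken on that day and treats other days separately, so it assumes that a PK day is a dosing day. The word *daily* in 6.2.1.1.2 leans the same way, as does Appendix A note j, which describes the Day 13 biomarker samples as pre-dose.

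Rest days carry safety weight in this design. Protocol 1.3.2 explains that five days on and two off replaced daily dosing so that platelets could recover in the off days. Under 5.2, an AM0010 reduction for Grade 3–4 thrombocytopenia or anemia is made only by adding rest days. A stray Day 13 dose would therefore take back part of the reduction in the patients who need it most.

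On Day 1 the issue is the meaning of the sample. A concentration drawn after a home dose is no longer a pre-dose value.

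**Working it through.** There is no planned figure to reproduce. The check lays the PK days against the dosing calendar and then counts doses and hours.

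**Step 1. Nominal PK days**

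| Sample | Cycles | Number | Status of the day | Fits a home dose before the draw? |
|---|---|---|---|---|
| Day 1 | 1, 2, 3, 5 | 4 | Dosing day; sample listed as pre-dose, dosing then described at the clinic | No |
| Day 13 | 1, 2, 4 | 3 | Rest day | No |

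Total 4 + 3 = 7. None of the seven fits the instruction.

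**Step 2. Visit window**

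The Day 13 visit may move by 3 days either way (6.2.1.1.3). With the next cycle starting on time, that covers seven calendar days: Days 10, 11, 12, 13 and 14, then Days 1 and 2 of the next cycle. On the full schedule, home dosing is right on Days 10, 11 and 12 and on the next Day 2 (4 of 7). Days 13 and 14 are rest days. The next Day 1 is a dosing day, but its sample should precede the dose. So 6.8.2 is correct for some moved visits and does not separate them from the nominal ones.

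**Step 3. Size if followed literally on Day 13**

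Count the next Day 1 as Day 15. The gap in hours from last dose to next cycle is (15 − last dosing day) × 24. With a Day 13 dose it is (15 − 13) × 24 = 48 on any schedule.

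| Schedule | Doses per cycle | With a Day 13 dose | Gap as planned | Gap with a Day 13 dose |
|---|---|---|---|---|
| Full (5 on, 2 off) | 5 + 5 = 10 | 11 | (15 − 12) × 24 = 72 h | 48 h |
| 80% (4 on, 3 off) | 4 + 4 = 8 | 9 | (15 − 11) × 24 = 96 h | 48 h |
| 60% (3 on, 4 off) | 3 + 3 = 6 | 7 | (15 − 10) × 24 = 120 h | 48 h |

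The 80% schedule drops 10 − 8 = 2 doses per cycle and the 60% schedule drops 10 − 6 = 4. One stray dose gives back one of two, or one of four.

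Two limits apply. Table 10 shows only Days 1–7, so the second week at 80% and 60% is assumed to repeat the first. The 60% level needs a recurrence on a later cycle (5.2), so its row cannot apply at Cycle 1 Day 13. At most there is one extra dose in each of three cycles.

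**The case against.** The strongest reply is that the usual manner simply means the usual schedule. The rest days are stated in several places, and nothing in 6.8.2 claims to override them. Patients are trained, and the diary is reviewed at every visit. A blood count with platelets is scheduled at these same Day 13 visits (6.2.1.1.3), hematology is checked before Day 1 dosing (6.2.1.1.1), and Grade 3–4 thrombocytopenia triggers a hold (5.2). Most of this stands: it makes an extra dose unlikely and limits its harm. It does not repair the text, because the dose-time sentence still presumes a dose that day. The Day 13 count is also only a partial safeguard, since it is taken around the time of the stray dose and may not show its effect.

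On Day 1, a reader might infer that up to three of the four samples (Cycles 2, 3 and 5) will in practice be post-dose. The documents do not support that. Under a heading covering Cycles 1–12, 6.2.1.1.2 describes dosing at the clinic. Although 5.1.1 and Appendix A note r tie supervised or staff dosing to the first dose, the natural order is pre-dose procedures, then dosing. What remains is that 6.8.2 contradicts that order.

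A reader might also connect a Day 13 dose with the 55% rate of Grade 3–4 thrombocytopenia reported in 1.3.2. That rate came from uninterrupted daily dosing. One added dose, with Days 6, 7 and 14 still off, is a different exposure.

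**Conclusion.** The conflict is real on the face of the current protocol. For nominal Day 13 in Cycles 1, 2 and 4, the PK instruction contradicts the rest-day rule. For Day 1, it does not fit a pre-dose sample followed by clinic dosing. On the full schedule the literal consequence is 11 doses instead of 10 in that cycle, and 48 hours instead of 72 before the next Day 1. The loss of rest is larger on a reduced schedule, given the assumed second-week pattern. An extra dose is a limited risk, not an expected event.

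A reader might go further and infer a measurable distortion of the PK results. The documents do not allow that to be sized. The delay from home dose to draw is not given, SAP section 13 does not say how concentrations will be grouped, and neither the separate PK plan nor the Lab Manual is available. Recorded dose times would also let a post-dose sample be modelled as such. The first interim analysis uses PK exposure, so no claim is made either way about its Go/No-Go decision.

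The OS analysis, alpha and power are unaffected. Severity is minor.

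**What to change.** In 6.8.2, replace the home-dosing sentence and the dose-time sentence after it with:

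> On PK sampling days patients follow their current AM0010 schedule; no AM0010 is taken on a rest day, including Day 13. On Day 1 the dose is given after the PK draw. If a visit within the window falls on another scheduled dosing day, the dose is taken as scheduled. The time of the most recent dose, and of any dose that day, is recorded.

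The sentence on diary dose times can stay. Deleting *daily* in 6.2.1.1.2 is an optional editorial tidy-up.

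The cost is small: no new visits, samples or CRF fields, because 5.1.3 already has the date and time of each dose recorded in the diary and on the CRF. A change to procedures needs IRB/IEC review under 11.2, across about 150 sites, so the wording is best carried in the next amendment, with a clarification to sites in the meantime.
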